5.3.3. Imputation rules for date of last contact and efficacy assessments

5.3.3.1. Date of last contact

The date of last contact will be derived for patients not known to have died at the analysis cut-off using the latest complete date among the following:

- All patient assessment dates (blood draws (laboratory, PK), vital signs, performance status, ECG, tumor assessments)
- Start and end dates of anti-cancer therapies administered after study treatment discontinuation
- AE start and end dates
- Last date of contact collected on the 'Survival Follow-up' eCRF (do not use date of survival follow-up assessment unless status is 'alive')
- Study drug start and end dates
- Randomization date

- Withdrawal of consent date
- Date of discontinuation on disposition eCRF pages (do not use if reason for discontinuation is lost to follow-up).

Only dates associated with actual examinations of the patient will be used in the derivation. Dates associated with a technical operation unrelated to patient status such as the date a blood sample was processed will not be used. Assessment dates after the cut-off date will not be applied to derive the last contact date.

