| 
16. Survival Assessment: All patients will be followed for survival and subsequent anticancer therapies every 3 months (± 14 days) after the last study clinic visit until death, end of the study, or patient withdrawal of consent, whichever comes first. These visits may be conducted in-clinic or by remote contact (eg, telephone). Additional timepoints to collect survival information may be requested by the Sponsor in preparation for interim and final analyses.
 |
| 
17. Patient-Reported Outcome Questionnaire: NCCN-FACT FBISI-18 and EQ-5D-5L are to be administered at the End of Treatment/Withdrawal visit and at the 30, 60 and 90 Day Follow-up Visits.
 |
| 
18. Banked Blood Biospecimens for Exploratory Assessments: Blood biospecimens (~24 mL) will be collected at the End of Treatment/Withdrawal visit and retained as whole blood, plasma, and serum (Prep D1: 4 mL K₂ EDTA whole blood collection optimized for DNA analysis; Prep B1: 10 mL K₂ EDTA blood for plasma preparation, and Prep B2: 10 mL blood for serum preparation), and retained in a biobank for exploratory biomarker assessments, unless prohibited by local regulation or by decision of the Institutional Review Board or Ethics Committee. See Section 7.5.2 and Section 7.6.
 |
| 
19. De Novo Tumor Biopsy: A de novo (ie, fresh biopsy) tumor sample should also be collected at End of Treatment/Withdrawal visit, unless clinically contraindicated. Tumor tissue from cytologic sampling (eg, fine needle aspiration, including formalin fixed, paraffin embedded [FFPE] cell pellet material) or bone metastases is not adequate and should not be submitted. The de novo biopsy should be formalin-fixed and paraffin-embedded as per routine procedures (see Laboratory Manual), and the resulting FFPE tissue block(s) should be submitted to the Central Laboratory. If an FFPE tissue block cannot be provided, 15 freshly cut unstained slides (10 minimum) will be acceptable.
 |
| 
20. Pharmacokinetics: Arm A ONLY: Blood samples (3.5 mL) for avelumab PK will be taken at the End of Treatment and 30 day Follow-up visits. Details are outlined in Section 7.3.
 |

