9.3.1. Analysis of Primary Endpoint

OS is defined as the time from the date of randomization to the date of death due to any cause. Patients last known to be alive will be censored at date of last contact.

The primary analyses of OS will be performed based on the Full Analysis Set. A stratified log-rank test (one-sided) stratified by stratification factors described in [Section 3](#) will be used within each comparison at the interim and/or final analyses with the overall significance level preserved at its respective levels (one-sided 0.015 for all patients and one-sided 0.01 for patients with PD-L1-positive tumors). OS time associated with each treatment arm will be summarized using the Kaplan-Meier method and displayed graphically where appropriate. Confidence intervals (CIs) for the 25th, 50th and 75th percentiles will be reported. The Cox proportional hazards model will be fitted to compute the treatment hazard ratios and the corresponding 95% CI.

OS will also be evaluated based on the PPS as a sensitivity analysis using the stratified log-rank test with the overall significance level preserved at its respective levels (one-sided 0.015 for all patients and one-sided 0.01 for patients with PD-L1-positive tumors).

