5. GENERAL METHODOLOGY AND CONVENTIONS

5.1. Hypotheses and Decision Rules

5.1.1. Hypotheses and sample size determination

The study is designed to test, in parallel, the following hypotheses:

$$H_{0 \text{ All patients}}: HR_{OS (Arm A/Arm B)} \geq 1, \text{ versus } H_{a \text{ All patients}}: HR_{OS (Arm A/Arm B)} < 1$$

$$H_{0 \text{ PD-L1+}}: HR_{OS (Arm A/Arm B)} \geq 1, \text{ versus } H_{a \text{ PD-L1+}}: HR_{OS (Arm A/Arm B)} < 1$$

where HR_{OS} represents the hazard ratio for OS in the experimental arm vs the control arm.

Approximately 668 patients will be randomized to the treatment arms using a 1:1 randomization, stratified by best response to chemotherapy (CR or PR vs. SD) and site of metastasis (visceral vs. non-visceral) at time of initiating first-line chemotherapy. The type 1 error rate will be split between the co-primary populations to preserve the overall type 1 error rate for the study at 0.025 one-sided. It is estimated that at least 50% of the randomized patients will have adequate tissue for analysis and be determined to have PD-L1-positive tumors.

The sample size for this study is determined based on the following assumptions:

- For all patients and patients with PD-L1-positive tumors receiving BSC alone after first-line chemotherapy, the median OS is 12 months (Powles et al, 2015).
- For all patients receiving avelumab + BSC after first-line chemotherapy, the median OS is assumed to be 17.1 months.

- For patients with PD-L1-positive tumors receiving avelumab + BSC after first-line chemotherapy, the median OS is assumed to be 18.5 months.

This corresponds to a hazard ratio (HR) of 0.7 for all patients and 0.65 for patients with PD-L1-positive tumors under the exponential model assumption.

For all patients, if the true HR is 0.7 under the alternative hypothesis, a total of 425 OS events will be required to have 93% power to detect a HR of 0.7 using a one-sided log rank test at a significance level of 0.015 and a 2-look group-sequential design with Lan-DeMets (O'Brien-Fleming) α -spending function to determine the efficacy boundary and a Gamma Family (-8) β -spending function to determine the non-binding futility boundary.

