For patients with PD-L1-positive tumors, if the true HR is 0.65 under the alternative hypothesis, then a total of 219 OS events will be required to have 80% power to detect a HR of 0.65 using a one-sided log rank test at a significance level of 0.01 and a 2-look group sequential design with Lan-DeMets (O'Brien-Fleming) α -spending function to determine the efficacy boundary and a Gamma Family (-8) β -spending function to determine the non-binding futility boundary.

The sample size further assumes a 5% drop-out rate for OS on either treatment arm, a non-uniform patient accrual accomplished over a 28-month period. The data cut-off for the primary OS analysis will occur after the target number of events has been reached in both co-primary populations and the last patient randomized in the study has been followed for at least 12 months after randomization.

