5.1.2. Decision rules

To protect the integrity of the study and to preserve the type I error rate, a fraction of alpha for efficacy will be spent at the interim analysis and accounted for in the overall type I error rate (if the interim analysis is performed exactly at the planned number of OS events, alpha spent at interim is 0.005 for all patients and 0.002 for patients with PD-L1-positive tumors). The significance levels for the interim and final efficacy analyses of OS will be determined by using the Lan-DeMets procedure with an O'Brien-Fleming stopping boundary. The overall significance level for the efficacy analysis of OS will be preserved at (one-sided) 0.015 for all patients and 0.01 for patients with PD-L1-positive tumors.

Two analyses will be performed for OS:

The interim analysis of OS will be performed after at least 315 of all randomized patients have died (74% of the target number of OS events for the 'all patients' population), and all of the following conditions have been met:

- 1) all initially planned patients have been randomized, and
- 2) at least 146 patients with PD-L1-positive tumors have died (approximately 66.7% of the total OS events expected in the 'patients with PD-L1-positive tumors' population).

The primary analysis of OS will be performed after at least 425 of all randomized patients and at least 219 patients with PD-L1-positive tumors have died, and the last patient randomized in the study has been followed for at least 12 months after randomization.

The study will have met its primary objective if the experimental arm is statistically significantly superior to the control arm for either one of the co-primary populations, either at the time of the interim analysis or at the time of the final analysis.

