5.2.1. Data handling after the cut-off date

Data after the cut-off date may not undergo the cleaning process and will not be displayed in any listings or used for summary statistics, statistical analyses or imputations.

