6.1. Primary Endpoint

6.1.1. Overall Survival

6.1.1.1. Primary Analysis

The following analyses will be based on the FAS using the strata assigned at randomization.

Overall survival (OS) is defined as the time from date of randomization to the date of death due to any cause. Patients last known to be alive will be censored at date of last contact.

$$\text{OS (months)} = [\text{date of death or censoring} - \text{date of randomization} + 1] / 30.4375$$

The primary analysis of OS will compare the OS time between the experimental arm and the control arm within each of the co-primary populations, and will be performed using a one-sided stratified log-rank test as described in [Section 5.1](#).

The treatment effect will be estimated using a Cox's Proportional Hazard model stratified by the randomization strata to calculate the hazard ratio. Each stratum will define a separate baseline hazard function (using the 'STRATA' statement in SAS PROC PHREG), ie for the i -th stratum the hazard function is expressed as: $h(i;t) = h(i,0;t) \exp(x\beta)$, where $h(i,0;t)$ defines the baseline hazard function for the i -th stratum and x defines the treatment arm (0=control arm, 1= experimental arm) and β is the unknown regression parameter.

Ties will be handled by replacing the proportional hazards model by the discrete logistic model (Ties=Discrete option in SAS PROC PHREG).

In order to account for the group sequential design in this study, the repeated CI (RCI) method ([Jennison and Turnbull, 2000](#)), will be used to construct the 2-sided RCIs for the hazard ratio at the interim and the final analyses of OS.

In addition, the unadjusted 95% CIs for the hazard ratio will also be reported at the interim and the final analyses for OS.

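### OS censoring discards proof of survival after the cut-off while earlier deaths count, which understates OS in both arms and can, if contact gaps differ by arm, tilt the test modestly

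*SAP*

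**What the plan says.** SAP 6.1.1.1 runs OS from randomization to death from any cause and states: "Patients last known to be alive will be censored at date of last contact". SAP 5.3.3.1 takes the last contact as the latest complete date among visits, laboratory draws, tumor assessments, AE dates, survival follow-up and similar sources, limited to actual examinations. It then states: "Assessment dates after the cut-off date will not be applied to derive the last contact date". SAP 5.2.1 is the general rule: data after the cut-off "will not be displayed in any listings or used for summary statistics, statistical analyses or imputations". Nothing says that a later contact with a living patient sets the censoring date to the cut-off.

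The same wording applies to both arms. On treatment, Arm A is dosed on site every 2 weeks (Protocol 5.4). Arm B has a clinic visit every 4 weeks and a Day 15 contact that may be by telephone (Schedule of Activities, treatment period, footnote 18). After treatment both arms have visits at 30, 60 and 90 days and then contacts every 3 months ±14 days. Footnote 16 of the follow-up schedule adds: "Additional timepoints to collect survival information may be requested by the Sponsor in preparation for interim and final analyses".

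The OS sensitivity analyses in SAP 6.2.2.2 (per-protocol, unstratified, and restricted mean survival if hazards are non-proportional) all keep this censoring rule.

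**The concern.** Take two patients last contacted two months before the cut-off and contacted again a month after it. One is found to have died before the cut-off: an event is added at the true date. The other is found alive: nothing is added, and the patient is censored two months early. Between last contact and cut-off, deaths are kept and survivors' time at risk is removed. This is informative censoring in the primary endpoint. It lowers the Kaplan-Meier medians and the 6- to 30-month OS rates, and shortens the reverse Kaplan-Meier follow-up.

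The comparison between arms is exposed only if the time removed differs by arm. The schedule makes that plausible: visits are more frequent in Arm A on treatment, and an arm that stays on treatment longer spends less time on 3-monthly contact. It could matter most at the interim, where more patients are alive and the primary objective was declared met (Protocol 1.2.3.3).

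**Working it through.** **Reproducing the design.** The significance levels are "one-sided 0.015 for all patients and one-sided 0.01 for patients with PD-L1-positive tumors". The SAP states "a total of 425 OS events will be required to have 93% power to detect a HR of 0.7" and "a total of 219 OS events will be required to have 80% power to detect a HR of 0.65". For a single look, power = Φ(½√D·|ln HR| − z₁₋α):

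- All patients: ½√425 × 0.3567 = 3.677; 3.677 − 2.170 = 1.506; power 93.4%.
- PD-L1-positive: ½√219 × 0.4308 = 3.188; 3.188 − 2.326 = 0.861; power 80.5%.

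With two looks and O'Brien-Fleming-type spending, power is 93.1% and 80.2%, and the interim limits are 2.595 and 2.947, as in SAP Table 5. The final limit for all patients is 2.210. The design reproduces.

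**Simulation.** Inputs from the documents: 668 patients, 1:1, accrual over 28 months, control median 12 months, 425 deaths at the final analysis with at least 12 months' follow-up, and for the interim "The interim analysis of OS will be performed after at least 315 of all randomized patients have died" with all patients randomized. Contacts followed the schedule: every 14 days (A) or 28 days (B) on treatment, then 30/60/90 days, then 3-monthly ±14 days. Survivors were censored either at the cut-off or at the last scheduled contact before it, on the same simulated data, with 6,000-8,000 trials per scenario.

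Assumptions not in the documents: exponential OS; accrual shape (uniform and ramp-up tried); all deaths up to the cut-off known; Arm B Day 15 calls not counted; stratification ignored. Median time on treatment is also not given. The Arm B value of 5.3 months is the placebo-arm PFS of the maintenance trial cited in Protocol 1.2.3.1; the A/B pairs tried were 5.3/5.3, 7.6/5.3 and 9/3 months.

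Results with uniform accrual (final analysis at month 40, ie 12 months after the last patient; negative Z favours avelumab):

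| True HR, look | A/B months on treatment | Mean gap, days A/B | Hazard inflation A/B | Z shift |
|---|---|---|---|---|
| 1.0, interim | 5.3/5.3 | 27.2/29.8 | 5.3%/5.8% | −0.045 |
| 1.0, interim | 7.6/5.3 | 23.9/29.8 | 4.6%/5.8% | −0.105 |
| 1.0, interim | 9/3 | 22.3/33.5 | 4.3%/6.6% | −0.207 |
| 1.0, final | 5.3/5.3 | 44.4/44.9 | 2.8%/2.8% | −0.003 |
| 1.0, final | 7.6/5.3 | 40.4/44.9 | 2.5%/2.8% | −0.032 |
| 1.0, final | 9/3 | 38.3/48.3 | 2.4%/3.0% | −0.073 |
| 0.7, final | 5.3/5.3 | 44.9/45.0 | 3.5%/2.8% | +0.004 |
| 0.7, final | 7.6/5.3 | 41.1/44.9 | 3.2%/2.8% | −0.027 |
| 0.7, final | 9/3 | 39.0/48.2 | 3.0%/3.0% | −0.068 |

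Cutting off at the 425th death without the 12-month minimum gives somewhat larger effects: hazard inflation up to 4.7%, Z shift to −0.14 at HR=1 and −0.09 at HR=0.7.

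**Hand check of one row (HR=1, interim, 7.6/5.3, month 28, drop-out ignored).**

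- Rate λ = ln 2/12 = 0.05776 per month.
- Surviving fraction = (1 − e^(−28λ))/(28λ) = 0.4956. Of 334 per arm, 165.5 are alive and 168.5 dead.
- Person-time = 168.5/0.05776 ≈ 2,917 months per arm.
- Time removed: A 165.5 × 23.9/30.4375 = 130 months; B 165.5 × 29.8/30.4375 = 162 months.
- Inflation: A 2,917/(2,917 − 130) = 1.047; B 2,917/(2,917 − 162) = 1.059.
- Z shift ≈ ln(1.0466/1.0588) × ½√337 = −0.0116 × 9.18 = −0.106, against −0.105 simulated.

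**Effect on error rates (HR=1).** Shifting the critical value:

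- Interim limit 2.595: 0.0047 becomes 1 − Φ(2.595 − 0.207) = 0.0085 at worst, and 0.0054 with a shift of 0.045.
- Single-look 0.015 level: 1 − Φ(2.170 − 0.142) = 0.021 at worst; 1 − Φ(2.170 − 0.073) = 0.018 with the 12-month minimum.

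**Equal gaps.** With gaps spread over 3 months in both arms, the Z shift is 0.000 at HR=1 and +0.010 at HR=0.7, although hazards rise by about 4-5%. With gaps up to 28 days in both arms, as a sweep shortly before the cut-off would give, hazards rise by about 1% and Z does not move.

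**The case against.** A reader might infer that OS is understated more in Arm B and that the rule therefore favours avelumab. The documents do not support that. The rule is arm-neutral and equal gaps give no shift at HR=1. At HR=0.7 and the final analysis, Arm A's hazard is inflated as much or more, because more of its patients are alive to be trimmed. Any tilt rests on contact gaps and treatment durations that the documents do not give.

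The simulated difference in gaps may also be too large. AE dates, tumor assessments and dates of subsequent anti-cancer therapy count toward last contact but were not modelled. Therapy dates would add contacts mainly in whichever arm progresses sooner, and counting Arm B's Day 15 call would shrink the tilt.

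The protocol allows extra survival contacts before analyses, and its Amendment 4 summary gives more uniform time since last contact as a purpose. That answers the point if contacts are made shortly before the cut-off. They are optional, however, and a sweep after the cut-off does not help: its alive dates are discarded while the earlier deaths it finds count.

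Finally, SAP 5.2.1 could be read as also excluding deaths learned after the cut-off, which would remove much of the asymmetry. But the SAP defines the OS event by date of death, and nothing excludes a death dated before the cut-off because it was reported later.

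**Conclusion.** The point stands as a modest bias in how the primary endpoint is derived. OS is understated in both arms: hazards are inflated by roughly 2-5% at 425 deaths and 4-7% at 315, given scheduled contacts, no sweep just before the cut-off, and all deaths up to the cut-off known.

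An effect on the test is conditional. If Arm A is contacted more often, Z at HR=1 moves toward avelumab by 0 to about 0.2 at the interim and 0 to 0.14 at the final analysis. At HR=0.7, power at the final analysis changes by at most about 1 point. The chance of crossing at the interim moves more: from about 0.71 to 0.72 with equal treatment durations, and to 0.77 in the most unequal scenario.

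Nothing here shows that the reported interim result was materially affected; the documents give no contact gaps by arm.

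**What to change.** - **SAP 5.3.3.1:** state that if any contact after the cut-off documents the patient alive, or the death date is after the cut-off, OS is censored at the cut-off date; otherwise the last contact on or before the cut-off is used.
- **SAP 5.2.1:** add an exception for survival status only. Without it the two sections would conflict.
- **SAP Table 7 and the reverse Kaplan-Meier analysis:** use the same date. At present a compliant patient contacted early and then late can have a gap of 3 months plus 28 days, about 17 weeks, and be classed as lost to follow-up under the 16-week rule.
- **Reporting:** tabulate time from last contact to cut-off by arm. For the interim already performed, repeat the OS analysis with the new rule as a sensitivity analysis; for the final OS update, apply the rule directly.

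The cost is a few SAP sentences, a small programming change, and cleaning of survival-status dates after the cut-off, which SAP 5.2.1 now says may not be cleaned. Patients with no later contact at data extraction would still be censored early, so a survival sweep around the cut-off remains useful.

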5.3.3.2. Death date

Missing or partial death dates will be imputed based on the last contact date:

- If the date is missing it will be imputed as the day after the date of last contact
- If the day or both day and month is missing, death will be imputed to the maximum of the full (non-imputed) day after the date of last contact and the following:
 - Missing day: 1st day of the month and year of death
 - Missing day and month: January 1st of the year of death.

5.3.3.3. Tumor assessments

All investigation dates (eg, X-ray, CT scan) must be completed with day, month and year.

If there are multiple scan dates associated with an evaluation, ie, radiological assessments occur over a series of days rather than the same day, the choice of date of assessment could impact the date of progression and/or date of response. If there are multiple scan dates associated with an evaluation, the earliest of the scan dates associated with the evaluation will be used as the date of assessment.

If one or more investigation dates for an evaluation are incomplete but other investigation dates are available, the incomplete date(s) are not considered for calculation of the assessment date and assessment date is calculated as the earliest of all investigation dates (eg, X-ray, CT-scan).

If all measurement dates for an evaluation have no day recorded, the 1st of the month is used.

If the month is not completed, for any of the investigations for an evaluation, the respective assessment will be considered to be at the date which is exactly between the previous and the following assessment. If both a previous and following assessments are not available, this assessment will not be used for any calculations.

5.3.3.4. Date of start of new anti-cancer therapy

Incomplete dates for start date of new anti-cancer therapy (drug therapy, radiation, surgery) will be imputed as follows and will be used for determining censoring dates for efficacy

analyses and in the derivation of the end of on-treatment period. PD date below refers to PD date by investigator assessment.

- The end date of new anti-cancer therapy will be included in the imputations for start date of new anti-cancer therapy. If the end date of new anti-cancer therapy is
 - completely missing then it will be ignored in the imputations below
 - partially missing with only year (YYYY) available then the imputations below will consider 31DECYYYY as the end date of the new anti-cancer therapy
 - partially missing with only month and year available then the imputations below will consider the last day of the month for MMMYYYY as the end date of the new anti-cancer therapy

- For patients who have not discontinued study treatment at the analysis cut-off date, last dose of study treatment is set to the analysis cut-off date in the imputations below.

- If the start date of new anti-cancer therapy is completely or partially missing, then the imputed start date of new anti-cancer therapy is derived as follows:

- Start date of new anti-cancer therapy is completely missing

Imputed start date = min [max(PD date + 1, last dose of study treatment + 1), end date of new anti-cancer therapy]

- Only year (YYYY) for start of anti-cancer therapy is available

IF YYYY < Year of min [max(PD date + 1, last dose of study treatment + 1), end date of new anti-cancer therapy] THEN imputed start date = 31DECYYYY;

ELSE IF YYYY = Year of min [max(PD date + 1, last dose of study treatment + 1), end date of new anti-cancer therapy]

THEN imputed start date = min [max(PD date + 1, last dose of study treatment + 1), end date of new anti-cancer therapy]

ELSE IF YYYY > Year of min [max(PD date + 1, last dose of study treatment + 1), end date of new anti-cancer therapy]

THEN imputed start date = 01JANYYYY

- Both Year (YYYY) and Month (MMM) for start of anti-cancer therapy are available

IF

YYYY = Year of min [max(PD date + 1, last dose of study treatment + 1), end date of new anti-cancer therapy], AND

MMM < Month of min [max(PD date + 1 day, last dose of study treatment + 1 day), end date of new anti-cancer therapy]

THEN

imputed start date = DAY (Last day of MMM) MMM YYYY;

ELSE IF

```
      YYYY = Year of min [max(PD date + 1, last dose of study treatment + 1), end
      date of new anti-cancer therapy], AND
      MMM = Month of min [max(PD date + 1 day, last dose of study treatment + 1
      day), end date of new anti-cancer therapy]
    THEN
      imputed start date = min [max(PD date + 1 day, last dose of study treatment + 1
      day), end date of new anti-cancer therapy];
    ELSE IF
      YYYY = Year of min [max(PD date + 1, last dose of study treatment + 1), end
      date of new anti-cancer therapy], AND
      MMM > Month of min [max(PD date + 1 day, last dose of study treatment + 1
      day), end date of new anti-cancer therapy]
    THEN
      imputed start date = 01 MMM YYYY;
    ELSE IF
      YYYY < Year of min [max(PD date + 1, last dose of study treatment + 1), end
      date of new anti-cancer therapy]
    THEN
      imputed start date = DAY (Last day of MMM) MMM YYYY;
    ELSE IF
      YYYY > Year of min [max(PD date + 1, last dose of study treatment + 1), end
      date of new anti-cancer therapy]
    THEN
      imputed start date = 01 MMM YYYY.
```

